9.4.2. Primary Endpoint(s)

Immunogenicity Endpoints

For each NI comparison between post-dose 1 ($[9 \times 10^{10}$ vp, 2.5×10^{10} , 7×10^{10} vp, 3.5×10^{10} vp, or 1.25×10^{10} vp] versus 5×10^{10} vp), estimated humoral immune response differences will be expressed as ratios of GMCs of S-ELISA (GMC [9×10^{10} vp, 2.5×10^{10} , 7×10^{10} vp, 3.5×10^{10} vp, or 1.25×10^{10} vp]/GMC 5×10^{10} vp), 28 days post-dose 1 with corresponding 97.5% confidence interval (CI) (2-sided) (Type 1 error 0.0125 for each comparison).

Similarly, for each NI comparison between post-dose 2 ($[9 \times 10^{10}$ vp, 2.5×10^{10} , 7×10^{10} vp, 3.5×10^{10} vp, or 1.25×10^{10} vp] versus 1- or 2-doses of 5×10^{10} vp), estimated humoral immune response differences will be expressed as ratios of GMCs of S-ELISA (GMC [9×10^{10} vp, 2.5×10^{10} , 7×10^{10} vp, 3.5×10^{10} vp, or 1.25×10^{10} vp]/GMC 5×10^{10} vp), 28 days post-dose 1 or 14 days post-dose 2 with corresponding 97.5% confidence interval (CI) (2-sided) (Type 1 error 0.0125 for each comparison).

In both sets (1 dose and 2 doses) of comparisons above, 97.5% CIs (2-sided) for mean difference in log₁₀-transformed S-ELISA titers between 2 groups will first be calculated and then back-transformed to the original scale to obtain the GMC ratios and the associated 97.5% CIs (2-sided). Non-inferiority between the groups will be established if the 97.5% CI of the estimated GMC ratio of the groups entirely lies above 2/3.

In the 1-dose (dose 1 of the 2-dose regimen) and 2-dose set NI comparisons, hierarchical testing after administration of a single-dose and 2 doses will be applied independently, as reflected in the Decision Tree-based Hypothesis Testing (Figure 2 and Section 9.1). The non-inferiority analyses will be done on the NI analysis set.

- Note: If a large number of participants become infected during the study (as assessed eg, by N-seroconversion or by PCR confirmation) or are SARS-CoV-2 seropositive at baseline, the main study and sub-study participants (seronegative at baseline) may be combined.
- If the power of the combined main study and sub-study is less than 80% then seropositive subjects at baseline will be included in the analysis. Further details of the analysis will be provided in the SAP.

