3. SAMPLE SIZE DETERMINATION

The number of participants chosen is to provide sufficient power for the non-inferiority comparisons.

The following assumptions were made in the sample size determinations:

Log transformed (\log_{10} scale) immune response data are normally distributed

A common standard deviation (SD): SD=0.5 (\log_{10} scale) of the immune response log transformed data

Non-inferiority margin = $\log_{10}(2/3) = -0.176$

Alpha = 0.0125 (1-sided) for 1- and 2-dose NI comparisons

- Alpha = 0.025 (one-sided). Using a Bonferroni correction, Type I error will be split equally over the 1-dose and 2-dose comparisons: 0.0125 (1-sided) for 1- and 2-dose NI comparisons

Power = 90%

Based on the above assumptions, and approximately a 10% dropout, a sample size of 225 participants per active vaccine group (see [Table 2](#)) is needed to detect non-inferiority of testing 1-dose and 2-doses of 9×10^{10} vp, 2.5×10^{10} vp, 7×10^{10} vp, 3.5×10^{10} vp, and 1.25×10^{10} vp Ad26.COV2.S as the test groups versus 1-dose and 2-doses of 5×10^{10} vp Ad26.COV2.S (release titer) as the reference groups, with 90% power (main study sample size assessment).

The originally intended NI population was comprised of participants from the main study who were SARS-CoV-2 seronegative at baseline and non-previously vaccinated. In addition, participants becoming infected with SARS-CoV-2 during the study are excluded from this population from the time of infection.

Participants were screened using a local SARS-CoV-2 serology test to ensure only participants who were seronegative at baseline were enrolled in the main study. However, a preliminary blinded evaluation of central N-serology results in main study participants at Day 29 and Day 71 showed that overall, 27% and 38% of participants, respectively, were N-serology positive at these time points. The higher-than-expected N-serology positive status at Day 29 and Day 71 indicated that participants became infected during the study and/or local serology tests were not sufficiently sensitive, affecting the power of the study.

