For the sub-study (initiated to further characterize the innate, pro-inflammatory and other relevant (e.g., prothrombotic) responses to Ad26.COV2.S to better understand a possible risk to TTS events), a target of approximately 240 participants will be enrolled and will receive a 2-dose vaccination regimen at either 9×10^{10} vp, 2.5×10^{10} vp, 5×10^{10} vp, or 1.25×10^{10} vp. As participants in the sub-study share common blood sampling timepoints with the main study, data from both cohorts can be merged for analyses. Due to the higher-than-expected N serology positive results in the main study affecting the power of the study, the non-inferiority assessment will combine participants from the main study and sub-study.

Table 4 below shows how, when combining main and sub study participants (randomized as SARS-CoV-2 seronegative at baseline based on local serology by finger prick testing), the power is affected due to a hypothetical 10%, 20%, 30%, 40%, 50% and 60% loss of evaluable participants (lost due to various reasons, e.g. lost to follow-up, participants with major protocol deviations with impact on immunogenicity, participants who become infected with SARS-CoV-2, participants who received their vaccination outside the allowed window, etc.).

Table 4: Impact of loss of evaluable subjects on NI assessment power

Dose level	Sample size at enrollment per arm (main study + sub study)	Group	% loss of evaluable participants since enrollment					
			10%	20%	30%	40%	50%	60%
9x1010 vp	265(225+40)	1	94%	91%	87%	81%	73%	62%
2.5x1010 vp	265(225+40)	5	94%	91%	87%	81%	73%	62%
7x1010 vp	225 (225+0)	2	90%	86	81%	74%	65%	54%
5x1010 vp	265(225+40)	3	94%	91%	87%	81%	73%	62%
3.5x1010 vp	225 (225+0)	4	90%	86	81%	74%	65%	54%
1.25x1010 vp	265(225+40)	6	94%	91%	87%	81%	73%	62%

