5.5.3.1. Non-Inferiority Analysis- Immune Response

Formal NI testing will be applied to demonstrate non-inferiority of immunogenicity. Non-inferiority will be analyzed by vaccine dose levels. As described in section 4, only one of the two scenarios will be considered for non-inferiority hypothesis testing at primary analysis. If there is an overall loss of $> 40\%$ evaluable data points in the NI set at Day 29 (defined as number of evaluable participants in the NI set at D29/total number of subjects in Table 4), the population in scenario 2 will be used for primary analysis.

- **Scenario 1 (base case scenario):** non-inferiority will be performed on the NI set including participants from the main and the sub study. A linear regression analysis with only one main effect (dose level) will be fitted, with log-transformed (\log_{10} scale) SARS-CoV-2 S-protein specific antibody concentration (S-ELISA) as the response variable and dose level as the independent variable.
- **Scenario 2:** Non-inferiority will be performed on the PPI set including participants from the main study and sub-study. A linear regression analysis with two main effects (dose level and SARS-CoV-2 serostatus at baseline) will be fitted, with log-transformed (\log_{10} scale) SARS-CoV-2 S-protein specific antibody concentration (S-ELISA) as the response variable and dose level and SARS-CoV-2 serostatus at baseline as the independent variables.

Participants with missing serostatus at baseline will not be included in this analysis.

Level of Significance

For each of the 1-dose and 2-dose vaccine regimens hypothesis, the type I error rate α will be set to 0.0125 (1-sided) and non-inferiority (NI) tests will be confirmed by constructing the corresponding 97.5% confidence interval (2-sided) which is equivalent to using $\alpha = 0.025$ (1-sided) with 98.75 (1-sided CI).

Multiplicity Adjustment

The family-wise error rate (FWER) at $\alpha = 0.025$ (one-sided), will be controlled by:

Splitting the Type I error rate $\alpha = 0.025$ into two (i.e., $\alpha = 0.0125$) using Bonferroni correction for the independently tested 1 and 2 doses NI hypotheses (see

[Figure 1](#)).

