Where the pooled variance estimate, $S_p^2 = \frac{(n_g-1)s_g^2 + (n_r-1)s_r^2}{n_g+n_r-2}$ and $v_p = n_g + n_r - 2$ is the degrees of freedom for the t-distribution and $\alpha = 0.0125$.

Since log transformation is monotone, back transforming confidence intervals for the difference in means in the log scale gives a confidence interval for the ratio of the geometric means. Hence, the lower and upper bounds of the 2-sided $(1 - \alpha)\%$ confidence interval for the GMC ratios are as follows:

$$\begin{aligned} ((GMC\ Ratio))_{Lower\ Bound} &= 10^{\left(\bar{X}_g - \bar{X}_r - t_{(1-\alpha/2; v_p)} S_p \sqrt{\left(\frac{1}{n_g} + \frac{1}{n_r}\right)}\right)} \\ ((GMC\ Ratio))_{Upper\ Bound} &= 10^{\left(\bar{X}_g - \bar{X}_r + t_{(1-\alpha/2; v_p)} S_p \sqrt{\left(\frac{1}{n_g} + \frac{1}{n_r}\right)}\right)} \end{aligned}$$

For each of the vaccine dose level, g comparisons (post-dose 1 and post-dose 2), NI will be demonstrated if

$$((GMC\ Ratio))_{Lower\ Bound} > \frac{2}{3}$$

If the assumptions of the unknown equal variances for the independent normal distributions of vaccine dose levels do not hold (i.e., test of equality variances shows that the variances are significantly different), then an approximate t-distribution with Satterthwaite approximated degrees of freedom will be used instead of (6) (Casella, G & Berger L.R (1990)).

SAS v 9.4 will be used in implementing the above NI comparisons.

Remarks:

No generally accepted immunological correlate of protection has been demonstrated for SARS-CoV-2 to date. If a correlate or threshold for protection against COVID-19 is established in terms of humoral immunity, then a statistical comparison to that correlate or threshold will be performed in addition, as outlined in a revised analytical plan. If the correlate or threshold of protection will be used as an endpoint the definition of seroconversion and seroconversion rate will be described in Section 5.7.

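### SAP 5.5.3.1 gives two different bounds for the primary non-inferiority decision: a 97.5% two-sided interval in words, a 98.75% two-sided interval in the formula

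*SAP*

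**What the plan says.** The level is stated in several places, and they agree except for the formula.

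- SAP 3 (Sample Size Determination): "Alpha = 0.0125 (1-sided) for 1- and 2-dose NI comparisons", from a Bonferroni split of one-sided 0.025. Protocol 9.2 has the same split.
- Protocol 9.4.2: "Non-inferiority between the groups will be established if the 97.5% CI of the estimated GMC ratio of the groups entirely lies above 2/3".
- SAP 5.5.3.1, Level of Significance: one-sided 0.0125, confirmed by "constructing the corresponding 97.5% confidence interval (2-sided) which is equivalent to using" one-sided α = 0.025 with a 98.75% one-sided interval.
- SAP 5.5.3.1, formula: a two-sided (1-α) interval, mean difference ± t(1-α/2; v_p) × S_p × sqrt(1/n_g + 1/n_r), where v_p "is the degrees of freedom for the t-distribution and $\alpha = 0.0125".
- SAP 5.5.3.1, decision rule: "For each of the vaccine dose level, g comparisons (post-dose 1 and post-dose 2), NI will be demonstrated if" the lower bound from that formula exceeds 2/3. The section then adds: "SAS v 9.4 will be used in implementing the above NI comparisons".

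The same section specifies a linear regression for both analysis scenarios. For Scenario 2, "A linear regression analysis with two main effects (dose level and SARS-CoV-2 serostatus at baseline) will be fitted". No confidence level is tied to the regression contrasts separately.

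**The concern.** A one-sided α has been put into a two-sided formula. With α = 0.0125, t(1-α/2) leaves 0.00625 in the lower tail, half of what the words, the protocol and the sample size require. Nothing in the SAP redefines α for the formula or says that a 98.75% two-sided interval is intended.

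The sentence beside the formula does not settle the matter, because it is itself wrong: a 98.75% one-sided interval corresponds to one-sided 0.0125, not 0.025. One subsection therefore attaches 0.0125, 0.025 and, by implication, 0.00625 to a single decision.

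What is at stake is power and a single verdict per dataset. Type I error is not inflated. But if the formula is coded as printed, the trial is weaker than planned at every step, and in a fixed sequence the losses accumulate. Power was already under pressure: SAP 3 reports 27% and 38% N-serology positive at Days 29 and 71, which led to the pooling of the sub-study and the reordered tests. Having to choose between two bounds after unblinding would also be open to challenge.

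**Working it through.** **Inputs.** SD 0.5 (log10), margin log10(2/3) = -0.1761, one-sided 0.0125, 90% power (SAP 3, protocol 9.2); 225 per group with 10.2% dropout (protocol 9.2), so 225 × 0.898 = 202 evaluable. A true GMC ratio of 1 is assumed; the documents do not state it, but it reproduces their figures.

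**Method.** Power = P(T' > t(1-a; df)), where T' is noncentral t with df = n_g + n_r - 2 and noncentrality 0.1761 / [0.5 × sqrt(1/n_g + 1/n_r)], and a is the lower-tail probability.

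**Step 1: reproduce the plan.** The smallest n for 90% power at a = 0.0125 is 202 per group, and 202 / 0.898 = 224.9, so 225 as stated. (A normal approximation gives 201 and 224.) SAP Table 4, taking equal arms at 10% to 60% loss:

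| Arm size | Source | 10% | 20% | 30% | 40% | 50% | 60% |
|---|---|---|---|---|---|---|---|
| 265 | SAP Table 4 | 94 | 91 | 87 | 81 | 73 | 62 |
| 265 | a = 0.0125 | 94.4 | 91.5 | 87.4 | 81.2 | 72.8 | 62.1 |
| 265 | a = 0.00625 | 90.8 | 86.8 | 81.2 | 73.5 | 63.5 | 51.9 |
| 225 | SAP Table 4 | 90 | 86 | 81 | 74 | 65 | 54 |
| 225 | a = 0.0125 | 90.1 | 86.2 | 81.0 | 73.8 | 64.8 | 54.2 |
| 225 | a = 0.00625 | 84.8 | 79.6 | 73.1 | 64.8 | 54.7 | 43.8 |

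The table was built at 0.0125. The formula's level does not match it.

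**Step 2: critical values at 202 v 202 (df 402).** In words, t(0.9875) = 2.250. In the formula, t(1 - 0.0125/2) = t(0.99375) = 2.509.

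**Step 3: results that change verdict.** The smallest observed ratio that passes is 10^(-0.1761 + t × 0.5 × sqrt(1/n_g + 1/n_r)). At 202 v 202 the last factor is 0.5 × sqrt(2/202) = 0.04975.
- Words: -0.1761 + 2.250 × 0.04975 = -0.0642, ratio 0.863.
- Formula: -0.1761 + 2.509 × 0.04975 = -0.0513, ratio 0.889.

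At 159 v 159 the band is 0.892 to 0.922.

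**Step 4: power for one comparison.**

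| Evaluable (test v reference) | 97.5% interval | Formula as printed |
|---|---|---|
| 202 v 202 | 90.1% | 84.8% |
| 159 v 159 (40% loss of 265) | 81.2% | 73.5% |
| 135 v 159 (40% loss of 225 and 265) | 77.5% | 69.0% |

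The last row applies to the 7×10^10 and 3.5×10^10 vp groups, which have no sub-study participants. Under the printed formula, 90% power needs 232 evaluable per group; 232 / 0.898 = 258.4, so 259 enrolled.

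**Step 5: the post-dose 1 sequence.** Simulated probability of passing all five steps (400,000 runs, shared reference arm, pairwise pooled variance, ratio 1 for every dose):

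| Sizes | 97.5% interval | Formula as printed |
|---|---|---|
| 202 in every group | 71% | 60% |
| 10% loss of Table 4 sizes | 79% | 69% |
| 40% loss of Table 4 sizes | 50% | 38% |

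The ten-step post-dose 2 sequence was not computed.

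**Step 6: error rate.** Two families at 0.00625 each bound the family-wise rate at 0.0125, against the 0.025 allowed.

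**The case against.** The strongest reply is that the intended level is not in real doubt. The protocol gives the decision rule in plain words, the SAP repeats the 97.5% interval, and the sample size and Table 4 rest on one-sided 0.0125. One symbol stands against all of that, and a programmer who followed the words would be right. Nothing in the documents shows that anyone coded the formula literally, and the error is in the safe direction. This stands, and it limits the harm to a conditional loss of power.

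Second, the SAP names regression for both scenarios, so the two-sample formula may not be the operative analysis, and it cannot give the serostatus-adjusted contrast of Scenario 2. Scenario 2 takes over when more than 40% of evaluable data points are lost from the NI set at Day 29, so the 40%-loss figures sit at the edge of the formula's range. This also stands. It is a reason to state the level for the regression contrasts, not a reason to leave the formula as it is.

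Third, the sequence figures assume a ratio of 1 at every dose, including 1.25×10^10 vp. With illustrative ratios of 1.1, 0.9, 1.05, 0.95 and 0.8 in test order and 202 per group, five-step power would be about 21% with the 97.5% interval and 14% with the formula. Most of the shortfall would then come from the effects and the sequence. The single-comparison loss of about 5 points is the safer headline.

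None of this removes the contradiction. The section makes the formula's lower bound the decision rule for every comparison and refers the SAS implementation to it.

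**Conclusion.** The concern holds. The printed formula gives a 98.75% two-sided bound where the protocol, the SAP's own words, the sample size and Table 4 require 97.5%. The departure is conservative. If coded as printed, it costs about 5 points of power per comparison at 202 per group (90.1% to 84.8%) and 8 to 9 points at 40% loss of the Table 4 sizes, and it would change the verdict for observed ratios of about 0.863 to 0.889 at 202 v 202. These sizes rest on SD 0.5, a true ratio of 1 and the unadjusted two-sample comparison; they do not carry over as computed to Scenario 2. Because this is the stated rule for the primary hypotheses, it must be corrected before the comparisons are run.

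**What to change.** In SAP 5.5.3.1:

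1. Set α = 0.025 in t(1-α/2; v_p), or write t(1-0.0125; v_p), so that the lower limit of the 97.5% two-sided interval is compared with 2/3.
2. State that the same level applies to the dose contrasts from the regression models in Scenarios 1 and 2.
3. Correct the Level of Significance sentence: the 97.5% two-sided interval corresponds to a 98.75% one-sided interval at one-sided α = 0.0125.
4. As a clean-up, align the dose labels C and D (now 3.5×10^10 and 7×10^10 vp) with hypotheses 1c/1d and 2c/2d. The labels set no test order, so nothing else depends on this.

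If programs already exist, confirm that the critical value is about 2.25, not 2.51. The cost is SAP wording and that one check; data, sample size and protocol are unchanged.

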5.6. Secondary Humoral Immune Response Endpoints

5.6.1. Definition of Endpoint

The secondary humoral immune response_endpoints are (at all blood collection timepoints):

Seroconversion is defined as participant test positive at any timepoint while the participant was seronegative at baseline.

Main study:

Serological response to vaccination and binding antibody GMCs to SARS-CoV-2 S protein as measured by ELISA, or equivalent assay.

Antibody GMCs (S-ELISA).

The proportion of participants achieving seroconversion of serum antibody against the SARS-CoV-2 S protein by S-ELISA

Sub study

Serological response to vaccination and binding antibody GMCs to SARS-CoV-2 S protein as measured by ELISA, or equivalent assay.

Antibody GMCs (S-ELISA)

The proportion of participants achieving seroconversion of serum antibody against the SARS-CoV-2 S protein by S-ELISA

GMCs derivations will be based on log-transformed (\log_{10} scale) immune response (ELISA concentrations). This will be applied for both main study analysis and sub study analysis.

5.6.2. Estimand

Not applicable

5.6.3. Analysis Methods

Descriptive statistics (geometric mean and confidence intervals, or median and interquartile range Q1-Q3, as appropriate) will be calculated for all blood collection timepoints based on the log-transformed (\log_{10} scale) immune response (ELISA concentrations) data. Geometric mean fold-increase in titers over baseline and the corresponding 95% CI in the S-ELISA will also be calculated. Geometric mean fold increases will be derived by first calculating the means of each blood collection timepoint change from baseline (pre-first vaccination or pre-second vaccination) log-transformed (\log_{10} scale) immune response (ELISA concentrations) and then back-transforming to the original scale. Further analysis methods are described in Section 6.1.

5.7. Exploratory Analysis

Definitions and details about the analysis methods for exploratory humoral immunogenicity endpoints are given in Section 6.1.

Main study:

Exploratory analyses may be performed at the request of the sponsor on a subset of participants. If the subset selection is to be performed prior to primary analysis and is potentially unblinding, the selection will be carried out by an external unblinded party.

The following exploratory humoral immune responses to Ad26.COVID2.S may be performed on a subset of participants:

- SARS-CoV-2 neutralization as assessed by SARS-CoV-2 neutralization assays VNA (wtVNA and/or psVNA) including neutralization of emerging SARS-CoV-2 variants.
- SARS-CoV-2 binding antibodies against emerging SARS-CoV-2 variants as assessed by S-ELISA or equivalent assay Adenovirus neutralization.
- Functional and molecular antibody characterization including Fc-mediated viral clearance, avidity, Fc characteristics, immunoglobulin (Ig) subclass and IgG isotype.
- Analysis of circulating Spike protein
- Epitope-specificity characterization of antibodies.
- Cytokine profiling: Analysis of cytokines, chemokines, and other proteins of the innate or adaptive immune response in the serum or plasma.
- Passive transfer: Analysis of immune mediators correlating with protection against experimental SARS-CoV-2 challenge in a suitable animal model.

Correlations include but are not limited to :

- Correlation between ELISA (S-ELISA; EU/mL) and VNA (wild-type virus [wt]VNA and/or pseudovirion [ps]VNA, including emerging variants) titers at selected timepoints.
- Correlation between Adenovirus neutralization (Ad26 VNA) and S-ELISA or VNA(wtVNA and /or psVNA, including emerging variants) titers at selected timepoints

Occurrence of asymptomatic SARS-CoV-2 infection.

- The number of participants with positive non-S protein ELISA or equivalent assay (eg, nucleocapsid [N] protein ELISA).

Immune response in vaccinated individuals with prior or breakthrough infection.

- SARS-CoV-2 neutralizing titers in serum measured by a VNA (wild-type virus and/or pseudovirion expressing S protein)
- SARS-CoV-2-binding antibodies measured by ELISA: Analysis of antibodies binding to the SARS-CoV-2 S protein

Sub study

Humoral response to Ad26.COVID2.S may include the following

- SARS-CoV-2 neutralization as assessed by SARS-CoV-2 neutralization assays VNA (wtVNA and/or psVNA) including neutralization of emerging SARS-CoV-2 variants
- SARS-CoV-2 binding antibodies against emerging SARS-CoV-2 variants as assessed by S-ELISA or equivalent assay
- Adenovirus neutralization
- Functional and molecular antibody characterization including Fc-mediated viral clearance, avidity, Fc characteristics, immunoglobulin (Ig) subclass and IgG isotype
- Analysis of circulating Spike protein
- Epitope-specificity characterization of antibodies
- Cytokine profiling: Analysis of cytokines, chemokines, and other proteins of the innate or adaptive immune response in the serum or plasma.

Correlations include but are not limited to:

- Correlation between ELISA (S-ELISA; EU/mL) and VNA (wild-type virus [wt]VNA and/or pseudovirion [ps]VNA, including merging variants) titers at selected timepoint.
- Correlation between Adenovirus neutralization (Ad26 VNA) and S-ELISA or VNA (wtVNA and /or psVNA, including emerging variants) titers at selected time points.

Occurrence of asymptomatic SARS-CoV-2 infection.

- The number of participants with positive non-S protein ELISA or equivalent assay (eg, nucleocapsid [N] protein ELISA)

Immune response in vaccinated individuals with prior or breakthrough infection

- SARS-CoV-2 neutralizing titers in serum measured by a VNA (wild-type virus and/or pseudovirion expressing S protein)
- SARS-CoV-2-binding antibodies measured by ELISA: Analysis of antibodies binding to the SARS-CoV-2 S protein.

To evaluate the innate, pro-inflammatory and other potentially relevant responses to Ad26.COVID2.S vaccination at selected timepoints.

- Analysis of messenger ribonucleic acid (mRNA) expression levels of vaccine-induced innate responses including inflammatory and coagulation-related mediators.
- Analysis of cytokines, chemokines, and other protein- or lipid mediators of the innate immune response.

